Colonoscopies with intestinal biopsies will be performed in the MGH GI endoscopy suite by [name] and his colleagues. **Intestinal tissue from the terminal ileum and the transverse colon** will be obtained to assess epithelial integrity including evaluation of **tight junction proteins (claudins, zonula occludens-1, occludin)**, intraepithelial **adherens junction protein E-cadherin**, staining for **LPS within the mucosa and in the lamina propia for evidence of microbial translocation**, and characterization of **intestinal T cells and macrophages** using flow cytometry and *in situ* staining of cytokines associated with macrophage activation. The Ragon Tissue Platform was established to provide necessary infrastructure to conduct patient-based research investigating tissue specific immune responses against HIV.

Bowel preparation: After eligibility is confirmed the subject will prepare for the procedures. To maximize the thoroughness and safety of the procedure, the colon must be completely empty prior to colonoscopy. The procedure preparation will be as per the GI Procedure Unit SOP.

Sedation for colonoscopy: Administration of sedative drugs at colonoscopy and has drawbacks, including an increased rate of complications, higher cost, and longer recovery periods for patients. Some studies have demonstrated that routine use of conscious sedation does not seem to be necessary because some participants found the examination to be only modestly or not at all uncomfortable. However, some investigators have proposed that without conscious sedation, the rate of intubation of the cecum may decrease and the risk of missing adenomas and cancer may increase. The decision to administer sedative drugs prior or during colonoscopy will be made by the physician, taking into account the patient's wishes and his/her medical conditions.

Intravenous benzodiazepines are the usual premedications used for colonoscopy, either alone or with a narcotic. Midazolam (2-5 mg) and Fentanyl (50 - 150 mcg) are commonly used. The combination of benzodiazepines and narcotics may achieve sedation more smoothly but is associated with a greater risk of respiratory depression. All procedures will be performed in the MGH Endoscopy Unit and patients will be monitored (eg, blood pressure, pulse, oxygen saturation) both during and after the procedure. Subjects with a history of adverse reactions to conscious sedation will be excluded from the study.

Colonoscopy: With the patient in left lateral decubitus position, a long, flexible, lighted viewing tube (colonoscope) will be inserted through the rectum into the colon. The scope is advanced and maneuvered while the lumen and walls of the colon are visualized by projections onto a television screen. The colonoscope has channels through which instruments can be passed in order to the perform biopsies or to cauterize potential bleeding. Air, water, and suction can be applied to help provide a clearer visual field for inspection. The goal for this procedure is to reach the cecum and the terminal ileum, and to collect specimens from throughout the colon as well as terminal ileum. Landmarks that may help to determine if this has been achieved include visualization of the appendiceal orifice and the ileocecal valve. No more than 28 intestinal biopsies will be obtained for research. In the event that the gastroenterologist identifies an abnormal finding in the colon, additional biopsies may be obtained as appropriate. In the event that the gastroenterologist identifies polyps on colonoscopy prior to initiation of study medication or at the end of the randomized treatment study, the polyps will be removed.

Intestinal Alkaline Phosphatase (IAP) Measurement: During the colonoscopy procedure, luminal fluid will be collected to measure IAP. Luminal fluid is collected by injecting about 5 ml of saline

through the operating channel of the scope into the terminal ileum and then aspirating approximately 3-5ml of fluid into a specimen trap.

Abdominal CT scan: Each subject will also have a non-contrast enhanced CT scan of the abdomen. A 1cm cross-sectional CT scan of the abdomen at L4 will be obtained to determine visceral adipose tissue (VAT) area and abdominal subcutaneous adipose tissue (SAT) area as previously described⁴⁷

Anthropometric Measurements: Subjects' height and weight will be obtained and plotted on standard weight charts to determine percent of ideal body weight. Body mass index will be calculated. Anthropometric measurements of waist to hip ratio, leg circumference, arm circumference and neck circumference will be performed using a standardized technique⁴⁸. Waist-to-hip ratio will be determined from the circumferential measurements of the iliac waist and the hips at the level of the iliac crest taken with the patient standing.

Nutritional Status and Exercise Activity: Food records will be analyzed for protein, carbohydrate, and fats (Nutritional Data Systems, Minneapolis, MN). The Bouchard 3-Day Physical Activity Record will also be administered.

Transcriptomic profiling of circulating monocytes: RNA from sorted CD14+ monocytes from the blood will be converted into a cDNA library using Illumina TrueSeq RNA sample preparation kit followed by paired end 50 cycles sequencing by HiSeq. Data will be analyzed using TopHat and Cufflinks and visualized using CummRbund as described by Trapnell *et al*⁴⁹. These software tools will allow us to analyze the data sets for differences in transcriptional splice variants. For analysis, we will specifically examine differential expression of transcripts as well as perform pathway analysis using IPA Transcriptional Analysis (Ingenuity Systems).

Medical Record Review: Medical records will be reviewed for relevant clinical data for subjects who are currently followed at MGH or BWH for clinical care. Subjects who receive clinical care from external providers will be asked to sign a Release of Information form. We will request and/or review relevant medical history, laboratory results and treatment history for HIV and/or Hepatitis B and C.

Fecal Occult Blood Testing (FOBT) Using the Fecal Immunochemical Test (FIT): Participants in the Randomized Study of Teduglutide vs. Placebo will be given a FIT kit to perform the test at home 1 year after starting the study medication (6 months after the study is over) to screen for colorectal cancer. Participants will be asked to asked to collect a very small stool sample using a brush so that they do not directly handle the fecal material. Using the brush, subjects will place the sample on the collection card, place the card in an envelope provided and mail to the laboratory.

Functional Assessment:

Functional assessments/scales are required to differentiate HIV-associated neurocognitive disorders into asymptomatic neurocognitive impairment (ANI) and mild neurocognitive disorders (MND), per Frascati guidelines for HAND⁵⁰. Subjects will complete the Cognitive Function Instrument (CFI) which is designed to detect early changes in cognitive and functional abilities in individuals without clinical impairment and is a sensitive measure in tracking longitudinal changes in cognitive function among older individuals ⁵¹. The CFI contains 14 questions; the participant version will be used in this study. The Patient's Assessment of Own Functioning Inventory (PAOFI) questionnaire which is complementary to the CFI will be used (33 questions) ⁵². Questionnaires will be administered through REDCap using a Partners Encrypted iPad.

Mood Assessment

Mood will be assessed using the Centre for Epidemiologic Studies Depression scale (CES-D ⁵³); a score of \geq 16 is indicative of high depressive symptoms ^{13,54,55}. This scale will be important to test if the Teduglutide affects depressive symptoms and will be needed to identify possible confounding to cognitive performance. The scale will be administered through REDCap using a Partners Encrypted iPad.

Neurocognitive Assessment (administered by neurologist or neuropsychologist):

The neurocognitive battery will include tests assessing:

- a. Premorbid intelligence: WRAT 4 reading
- b. Attention/Working Memory: WAIS IV Digit Span; CalCAP Abbreviated Test Battery
- c. The speed of information Processing: WAIS III Digit Symbol, Trail making test-part A, Victoria Stroop Test Word and Color; CalCAP Abbreviated Test Battery⁵⁶.
- d. Delayed Verbal Learning and Recall: Hopkins verbal learning test 1-3 and delayed
- e. Motor Skills: Grooved Pegboards for dominant and non-dominant hands

f. Executive function: Trail making test-part B; Victoria Stroop Test Interference These tests have been previously proven to be sensitive to neurocognitive disturbances in HIV infection⁵⁷ and have standardized norms. The complete neurocognitive assessment is designed to last <1 hour, and will be performed at visit 4 in all subjects and also repeated at the final 6 month visit following completion of the interventional study. We will determine the z-score for each test using normative data, average z-scores from all tests, and create a composite cognitive deficit score for subjects at each timepoint. The data will be scored per tests' instructions, and scores will be entered into REDCap database.

Remuneration

Transportation to and from visits will also be additionally subsidized and a meal ticket as well as parking will be provided at each visit.

Participants who participate in only Baseline Study Part 1 (2-visit cross-sectional substudy) will receive \$75.

Participants who undergo Baseline Study Part 1 and Part 2, (4-visit cross-sectional substudy including colonoscopy, cardiac CTA and FDG-PET) will receive \$375.

Participants in the interventional Randomized Study of Teduglutide vs. Placebo study will receive up to \$825 for completion of study.

HIV-negative control participants who undergo testing for neurological substudy (2-visits cross-sectional substudy including cardiac CTA and FDG-PET) will receive \$125.

Pro-rated remuneration

- In addition to providing parking and assistance with transportation when needed, participants will receive up to \$825 for the Randomized Study of Teduglutide vs. Placebo:
- \$50 after the completion of screen visit 1
- \$25 after the completion of screen visit 2 (bionutrition).
- \$225 after completion of screen visit 3 (colonoscopy)
- \$75 after the completion of the baseline visit
- \$25 after each safety visit (1, 3 month)
- \$400 at the completion of the final study visits

Participants in the cross-sectional study will receive up to \$375:

• \$50 after the completion of screen visit 1

- \$25 after the completion of screen visit 2 (bionutrition)
- \$225 after completion of screen visit 3 (colonoscopy)
- \$75 after the completion of visit 4

Participants in the neurological substudy will receive up to \$125:

- \$50 after the completion of visit A
- \$75 after the completion of visit B

Costs

There will be no cost to the subject for participation in the study.

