*Multivariate modeling:* For outcomes TBR and plaque, to control for potential confounders, multivariate linear regression modeling will be used to identify factors independently associated with increasing TBR and increasing number of atherosclerotic plaque lesions. Similar methods will be applied for neurocognitive score and mood assessment to cerebral FDG-PET/CT. Model variable selection will be based on "change-in-estimate" method⁵⁸. Candidate covariates to be chosen for entry into our model include all covariates significant on individual univariate models (p<0.05), potential confounders, and biologically plausible covariates with established relationships to atherosclerosis. Colinearity among covariates will be identified and redundant covariates will be excluded from the model. Confounders will be identified by observing changes in effect estimate β ; colinearity will be identified by observing changes in effect estimate β ; as well as by using Variance Inflation Factor criterion. Regression diagnostics will be used to check if model assumptions are met⁵⁸. We will control for age, gender, race, smoking, lipids, diabetes mellitus, WRAT 4 reading versus educational years, and hypertension in addition to other potential confounders identified by methods above.

Between group comparisons: We will also assess differences in microbial translocation, mucosal immunity and GI permeability markers among those with coronary atherosclerosis vs. those without atherosclerosis and in those with elevated TBR (>1.8) vs. those without elevated TBR. 2 group comparisons will be performed using Student's T-test if the outcome variable is normally distributed. Distributions will be tested for normality using the Wilk-Shapiro test and examination of the histogram distributions. If the outcome variable is not normally distributed, we will consider appropriate transformation to approximate a normal distribution. Alternatively, if distributions are non-normal despite the applied transformation, we will use nonparametric Wilcoxon rank sum test to compare the 2 groups. All tests will be 2-sided, and a p < 0.05 will be considered statistically significant.

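### As written, the cognitive deficit composite includes WRAT 4, the premorbid-intelligence test that is also a candidate covariate; this modestly dilutes cross-sectional analyses that do not adjust for it

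*Combined protocol and SAP*

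**What the plan says.** Three statements in the combined protocol and SAP bear on this.

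- **The battery.** Section V, Neurocognitive Assessment, opens its list with "The neurocognitive battery will include tests assessing" and gives items a to f. Item a is "Premorbid intelligence: WRAT 4 reading". Items b to f cover current function: attention and working memory, processing speed, verbal learning and recall, motor skills and executive function.
- **The composite.** The same part says the team will standardise each test against norms, then "average z-scores from all tests, and create a composite cognitive deficit score for subjects at each timepoint". No test is excepted. The battery "will be performed at visit 4 in all subjects and also repeated at the final 6 month visit".
- **The model.** The Multivariate modeling paragraph of the Aim 1A analysis plan says "Similar methods will be applied for neurocognitive score and mood assessment to cerebral FDG-PET/CT". Its adjustment set includes "WRAT 4 reading versus educational years, and hypertension".

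No other section removes WRAT 4 from the composite, or from the covariates when the composite is modelled.

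**The concern.** A premorbid measure is useful because disease is not expected to move it. That makes it a sensible adjuster and a poor component of a score meant to capture deficit. The plan's wording gives WRAT 4 both roles.

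Two things follow. Where WRAT 4 is not in the model, the composite carries one component that should not respond to disease, so a real difference in current cognition looks smaller. Where WRAT 4 is in the model, part of the outcome is regressed on itself. That alters the size of the reported coefficients and the fit, even though it leaves the exposure's test alone.

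The comparisons at stake are small. Section III adds 15 HIV-negative controls for the neurological substudy, to look for an HIV-specific link to cognitive impairment. The neurological aim is exploratory and has no sample size calculation of its own.

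**Working it through.** The plan states no effect size or power for the composite, so there is no figure to reproduce. What can be checked is how much including WRAT 4 changes the score.

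**Number of scores, k.** The plan does not say how scores are counted. Reading items a to f with CalCAP counted once gives WRAT 4 (1), Digit Span and CalCAP (2), Digit Symbol, Trails A, Stroop Word and Stroop Color (4), Hopkins trials and delayed recall (2), Pegboard for each hand (2), Trails B and Stroop Interference (2): k = 13. Counting CalCAP in both its domains gives 14. Counting named instruments, with Trails A and B separate, gives 9. The weight of WRAT 4 is 1/k: 7.7% at 13, 7.1% at 14, 11.1% at 9.

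**1. Cross-sectional, not adjusted for WRAT 4.** Assumptions: every score has SD 1; the other m = k-1 scores correlate r with one another and r_w with WRAT 4; disease shifts those m scores equally and WRAT 4 not at all.

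- Variance without WRAT 4: v0 = (1 + (m-1)r)/m
- Variance with WRAT 4: v1 = (m(1 + (m-1)r) + 1 + 2m·r_w)/k²
- Ratio of standardised effects, with to without: (m/k)·√(v0/v1)

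At k = 13:

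| r | r_w | v0 | v1 | ratio | ratio² |
|---|---|---|---|---|---|
| 0.3 | 0.3 | 4.3/12 = 0.358 | 59.8/169 = 0.354 | 0.929 | 0.863 |
| 0.5 | 0.5 | 6.5/12 = 0.542 | 91.0/169 = 0.538 | 0.926 | 0.857 |
| 0.5 | 0.3 | 6.5/12 = 0.542 | 86.2/169 = 0.510 | 0.951 | 0.905 |
| 0.3 | 0.5 | 4.3/12 = 0.358 | 64.6/169 = 0.382 | 0.894 | 0.799 |

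In the first three rows WRAT 4 correlates with the other tests no more than they do with one another. The loss there is 5 to 7%, equivalent to about 10 to 14% of the sample. The last row (11%, 20%) needs WRAT 4 to correlate more with each test than those tests do among themselves. Under the same restriction on r_w, the formula gives losses of about 7 to 11% at k = 9 and 5 to 7% at k = 14.

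**2. Models that adjust linearly for WRAT 4.** Write the composite as C = (m·R + W)/k, where R is the mean of the other scores and W is WRAT 4. If R = a + bX + cW + e, then C = (m/k)(a + bX + e) + ((m/k)c + 1/k)W.

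- The exposure coefficient and its standard error are both multiplied by m/k, so t and p are identical.
- The WRAT coefficient gains 1/k by construction.

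A simulated data set (n = 60) for each k confirms this:

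| k | exposure coefficient, without → with | t, both | WRAT coefficient | R² |
|---|---|---|---|---|
| 9 | 0.379 → 0.337 | 4.83 | 0.264 → 0.345 | 0.418 → 0.504 |
| 13 | 0.301 → 0.278 | 3.69 | 0.461 → 0.503 | 0.505 → 0.563 |

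If the composite is the predictor instead, its coefficient is multiplied by k/(k-1), its t is unchanged, and its variance inflation factor against WRAT 4 rises (1.22 to 1.43; 1.63 to 1.85).

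**3. Randomised comparison of change.** Let each of the other 12 changes have SD 1 and mutual correlation ρ, and let WRAT change have SD s, no treatment effect and no correlation with the rest. The ratio of standardised effects is 1/√(1 + s²/(12(1 + 11ρ))).

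- s = 0: 1.000.
- s = 0.5, ρ from 0 to 0.4: 0.990 to 0.998.
- s = 1, ρ from 0 to 0.4: 0.961 to 0.992.

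With the plan's 27 evaluable per arm and 80% power assumed without WRAT 4, power with it is 76.8 to 79.8% for s = 0.5 to 1.

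**4. What removal does for premorbid confounding.** With r_w of 0.3 to 0.5, a 1-SD premorbid difference between groups shifts the mean of the other 12 scores by 0.30 to 0.50. Including WRAT 4 makes the shift (12r_w + 1)/13, that is 0.35 to 0.54. Removing it takes away only 0.04 to 0.05.

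**The case against.** The best defence is that the wording is loose and no one intended this. The score is called a deficit score, WRAT 4 is labelled premorbid, and the plan gives it a separate covariate role; a neuropsychologist might well build the composite from items b to f without being told. That may be so. But the stated rule covers every test, and an analyst following it would include WRAT 4.

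Several limits do stand.

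- A reader might infer that having the covariate inside the outcome invalidates the regression. It does not: the test of any exposure is unchanged when WRAT 4 is a linear covariate.
- The phrase setting WRAT 4 against educational years may mean that only one is used. If education is used, the overlap disappears and the dilution remains.
- A reader might carry the cross-sectional loss over to the teduglutide comparison. The documents do not support that. If WRAT 4 is stable over six months, it scales mean change and SD alike, and the standardised effect is untouched.
- The unadjusted analyses are partly inferred. The only explicit model for the composite is the multivariate one, and cognition is not among the secondary endpoints named for Aim 2. An HIV-versus-control contrast is envisaged in section III, but no unadjusted test of the composite is written down.

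The plan's collinearity rule, "Colinearity among covariates will be identified and redundant covariates will be excluded from the model", does not settle the matter. It concerns redundancy between covariates, not a covariate that is a component of the composite being modelled.

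**Conclusion.** The point holds as a modest defect in how the composite is defined. As written, WRAT 4 is averaged into a score of current deficit while also being a candidate premorbid adjuster.

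The practical loss is mainly in cross-sectional analyses that do not adjust for WRAT 4: about 5 to 7% of the standardised effect, resting on the assumed 13 scores, equal disease effect on the other tests, none on WRAT 4, and the correlations stated. The 11% figure, with its 20% sample equivalent, should not be quoted as typical. Where WRAT 4 is adjusted for, inference on the exposure is intact; what is distorted is its coefficient, the WRAT coefficient and R². For the randomised change comparison the effect is 0 to 4% at 13 scores if WRAT change is uncorrelated with the other changes.

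It would also be wrong to conclude that dropping WRAT 4 from the composite removes premorbid confounding. Nearly all of it remains in the other tests and has to be handled by adjustment. Since the aim is exploratory, this is a worthwhile improvement and not a threat to the trial's main result.

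**What to change.** In the Neurocognitive Assessment part of section V, define the composite as the average of z-scores from the current-function tests in items b to f, and list the scores that enter it, including whether CalCAP counts once or twice. Use WRAT 4 solely as the premorbid covariate.

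In the Multivariate modeling paragraph, keep the WRAT/education adjustment, state whether WRAT 4, educational years or both are used, and say whether the composite is the outcome or the predictor in the cerebral FDG-PET model.

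The cost is a sentence or two of text. No new data, visits or participants are needed, and composites already computed can be rebuilt from the stored test scores.

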[name] of the MGH Biostatistics Center has provided biostatistical consultation regarding power calculations and design for the proposed studies. [name] biostatistical support will continue to be readily available for randomization, data analysis, and manuscript preparation.

Statistical Analysis Plan:

Baseline Study Part 1: Biomarkers, Immunology and Intestinal Permeability Studies and **Baseline Study Part 2: Colonoscopy, Cardiac CTA and FDG-PET/CT Studies (Aim 1A):** The statistical approach to assess correlations between intestinal permeability and microbial translocation with innate immune activation and cardiovascular disease. For mechanistic modeling, we will perform bivariate exploratory analysis followed by multivariate linear regression models to explain the impact of microbial translocation on cardiovascular inflammation.

Univariate analysis: To identify relationships between GI epithelial integrity, markers of innate immune activation and markers of microbial translocation with cardiovascular markers of vascular inflammation (TBR measured by FDG-PET) and atherosclerosis (segments with plaque) in HIV-infected patients, we plan to use linear correlation coefficients for continuous predictor variables (Pearson correlation coefficients if variables are normally distributed or Spearman correlation coefficients if their distributions are non-normal) to assess bivariate relationships between cardiovascular imaging measurements and measured covariates hypothesized to be associated with atherosclerosis development and vascular inflammation.

*Multivariate modeling:* For outcomes TBR and plaque, to control for potential confounders, multivariate linear regression modeling will be used to identify factors independently associated with increasing TBR and increasing number of atherosclerotic plaque lesions. Similar methods will be applied for neurocognitive score and mood assessment to cerebral FDG-PET/CT. Model variable selection will be based on "change-in-estimate" method⁵⁸. Candidate covariates to be chosen for entry into our model include all covariates significant on individual univariate models (p<0.05), potential confounders, and biologically plausible covariates with established relationships to atherosclerosis. Colinearity among covariates will be identified and redundant covariates will be excluded from the model. Confounders will be identified by observing changes in effect estimate β ; colinearity will be identified by observing changes in effect estimate β ; as well as by using Variance Inflation Factor criterion. Regression diagnostics will be used to check if model assumptions are met⁵⁸. We will control for age, gender, race, smoking, lipids, diabetes mellitus, WRAT 4 reading versus educational years, and hypertension in addition to other potential confounders identified by methods above.

Between group comparisons: We will also assess differences in microbial translocation, mucosal immunity and GI permeability markers among those with coronary atherosclerosis vs. those without atherosclerosis and in those with elevated TBR (>1.8) vs. those without elevated TBR. 2 group comparisons will be performed using Student's T-test if the outcome variable is normally distributed. Distributions will be tested for normality using the Wilk-Shapiro test and examination of the histogram distributions. If the outcome variable is not normally distributed, we will consider appropriate transformation to approximate a normal distribution. Alternatively, if distributions are non-normal despite the applied transformation, we will use nonparametric Wilcoxon rank sum test to compare the 2 groups. All tests will be 2-sided, and a p < 0.05 will be considered statistically significant.

Sample Size Determination: With 70 HIV-infected patients and 20 uninfected controls, we can detect a bivariate correlation Pearson's coefficients of at least 0.58, 0.33, and 0.29 can be detected at a 5% significance level with 80% power within uninfected, infected, and both the uninfected and infected subjects respectively. The detectable effect sizes of markers between elevated - and without elevated TBR groups will depend on the distribution of the observed TBR and the markers' distributions. If the rate of elevated TBR is 50% among the whole cohort of 70 patients, then an effect size with Cohen's effect size d>0.68 can be detected by a two-sided independent samples t-test at a 5% significance level with 80% power.

RNA Sequencing Subset (Aim 1B):

Statistical Analysis Plan: The BioConductor package LIMMA will be used to identify genes which are differentially expressed between the two compartments. Holm's and Benjamin-Hochberg methods will be applied for correcting multiple testing. *Sample Size Determination*: For *RNA-Seq* analysis using 7 patients with CVD and 7 without, there will be 27,000 genes to be included in the initial testing of which about 140 genes are expected to be differentially expressed significantly with a two to three times of the standard deviation of the fold difference in the expression levels. With a targeted false discovery rate (FDR) of 20% or less, the power to detect at least 112 differentially expressed genes significantly with an effect size of 2.7×SD with p<0.0011 (i.e., multiple testing adjusted alpha=0.0011) will be at least 80%.

Randomized Study of Teduglutide vs. Placebo (Aim 2):

Statistical Analysis Plan: For the primary outcome assessment, intention to treat principle will be applied in the analysis of this randomized placebo-controlled trial. For analysis of our primary outcome of arterial inflammation, we will compare the mean changes in arterial inflammation as assessed by FDG-PET measured as target to background ratio (TBR) of standardized uptake value in the group is randomized to teduglutide to the group that is randomized to placebo using independent samples t-test. Secondarily, we will also examine whether or not the mean of within group changes during the intervention period is zero using paired sample t-test. For secondary endpoints including change in markers of intestinal permeability, innate immune activation and microbial translocation, we will use the independent samples t-test to compare the means of the changes between the teduglutide group and the placebo group. In addition, longitudinal linear mixed effects modeling will be applied. The model will include random subject level intercept, fixed discrete time and group, and time \times group interaction term to characterize the within-group longitudinal means and to compare the between group difference in those longitudinal means. Effects of the potential confounders, (lipids, age, gender, smoking, diabetes mellitus, hypertension and other cardiovascular risk factors that may be different between the groups), will be adjusted by including them in the model as the covariates. We will utilize all available observations for this modeling even if there are some patients who have missing data at any time. If necessary, we will also perform Markov Chain Monte-Carlo (MCMC) based multiple imputation procedure.

Sample Size Determination: With 30 patients in each group and up to 10% attrition (i.e. evaluable n=27/group), this trial can detect at least a between group difference of 0.2244 in the two within person TBR mean changes at a 5% significance level with 85% power by a two-sided independent samples t-test. This assumed that the standard deviation of the within subject TBR change is 0.27, which was estimated from our prior study at MGH study of similar patient population²⁸ of which the observed mean \pm (standard deviation) of the cross sectional TBR data was 2.24 (\pm 0.35) and the assumed pre- to post intervention longitudinal correlation was 0.7. This detectable effect size is close to 10% of the baseline mean 2.24, and we anticipate that the placebo group will show no change (or even increase its mean value). The effect size of 10% is of clinical significance as it is similar to the amount of decrease seen with statin treatment for 3 months⁵⁹, the most effective medical therapy we have to date for treatment of atherosclerotic disease and prevention of MI.

VII. Risks and Discomforts

Colonoscopy: Colonoscopy are generally safe procedures and complications are rare. Given the underlying HIV infection of the study participants, there is potential for the sequellae of the endoscopy complications outlined below to be more serious and more difficult to treat.

Perforation: The risk of perforation of the colon is 0.2-0.4% after diagnostic colonoscopy and 0.3-1.0% with polypectomy. A higher rate (4.6%) is associated with hydrostatic balloon dilatation of colonic strictures. Perforation is more common (1) in patients who are oversedated or under general anesthesia, (2) in the presence of poor bowel preparation, or (3) with acute bleeding, and generally results from mechanical or pneumatic pressure or from biopsy techniques. Mechanical perforation by the tip of the instrument occurs at sites of weakness of the intestinal wall (eg, diverticula, transmural inflammation) and proximal to obstructing points (eg, neoplasms, strictures). Pneumatic perforation of the colon or ileum results from distension by insufflated air. Perforation from polypectomy is an electrosurgical injury. Free perforation into the peritoneal cavity may be recognized during the procedure if abdominal viscera become visible. A laceration so large that it can be observed directly through the colonoscope is a surgical emergency. In less severe situations, marked persistent abdominal distension or pain should prompt the ordering of radiographs; this imagery may reveal free air in the peritoneal perforation, usually a pneumatic injury, can give rise to subcutaneous emphysema. Fever and leukocytosis may eventually

develop with any of these perforations. When plain abdominal or chest radiographs show pneumoperitoneum, gross extravasation should be assessed; if present, surgical intervention is required. In the absence of leakage, treatment with intravenous antibiotics and close observation may be considered. This is a clinical determination.

Bleeding: Bleeding complicates approximately 1 of every 1000 colonoscopic procedures. Most cases resolve spontaneously. Following polypectomy, bleeding may occur immediately, but, in 30-50% of cases, it is delayed from 2-7 days until the eschar sloughs. Immediate bleeding can be treated by resnaring the remaining stalk and tightening the snare for 10-15 minutes, usually without further electrocoagulation. Another procedure that may be helpful is the injection of 5-10 mL of a 1:10,000 epinephrine solution into the stalk or the submucosa to achieve vasoconstriction. Delayed bleeding usually stops spontaneously, although transfusions, endoscopic therapy, angiography, and even laparotomy may be required in more severe cases.

Infection: Documented instances of transmission of infection from one patient to another or to endoscopic personnel are extremely rare. Bacteria reported to have spread include *Salmonella* species, *Pseudomonas* species, and *Escherichia coli*. Transmission of hepatitis B or C or HIV is extremely rare and has been linked to improper disinfection of scopes and accessories. With proper disinfection, there is no evidence that endoscopy presents a risk of hepatitis or HIV transmission.

Abdominal distension: Intestinal distension during endoscopy can cause notable discomfort and may also impair mucosal blood flow. Carbon dioxide rather than air insufflation during colonoscopy may offer some advantages, i.e., it is absorbed from the colon, it is nonexplosive, and mucosal blood flow is less affected, thus decreasing the risk of colonic ischemia.

Splenic rupture: Although a very uncommon complication, the presumed mechanisms of splenic rupture during colonoscopy include direct trauma to the spleen, marked angulation of the splenic flexure, excessive splenocolic ligament traction, and decrease in the relative mobility between the spleen and the colon. Hemodynamic instability, clinical features of acute abdomen, leukocytosis, and/or acute anemia in patients with persistent abdominal pain after colonoscopy demand immediate attention. Intestinal perforation or bleeding must first be excluded, after which CT scans can be used for further evaluation.

Small bowel obstruction: Small bowel obstruction is another rare complication of colonoscopy, although it is perhaps more common in patients who have a history of abdominal surgery and postoperative adhesions. The mechanism is uncertain, but it may occur secondary to air insufflation into the small bowel as a result of an incompetent ileocecal valve causing distension and entrapment of the small bowel by adhesions. Colonoscopists should be aware of this possible complication, particularly as skills improve and the ileum is intubated more frequently. Patients with a history of abdominal surgery or bowel obstruction should be informed of this complication when consent is given.

Medication effects: Sedatives used during colonoscopy may cause complications from allergic reactions or, more importantly, from doses that may be excessive for certain individuals and lead to respiratory depression. Serious events may complicate up to 0.5% of procedures. More than 50% of deaths associated with endoscopy are related to cardiopulmonary events. Adverse effects of benzodiazepines, other than respiratory depression, include anxiety and occasional injection-site reaction; the latter are more frequent with diazepam than with midazolam. Other adverse effects of narcotics include nausea, vomiting, and hypotension. Naloxone and flumazenil readily reverse the adverse effects of administration of these drugs, together with continuous monitoring of the sedated patient, can help minimize complications.

Simethicone: Simethicone is available over the counter and is generally considered safe. Simethicone is not absorbed into the body. Side effects are rare and include mild diarrhea, regurgitation, nausea, vomiting, bloating, heartburn, and constipation.

Magnesium Hydroxide: Magnesium Hydroxide is available over the counter and is generally considered safe. Side effects are rare and include diarrhea, upset stomach, stomach cramps, and vomiting.

Teduglutide:

In a published randomized placebo-controlled trial of teduglutide for 24 weeks in patients with short bowel syndrome, teduglutide was well-tolerated, safe and facilitated reductions in parenteral support in these patients⁴¹. In the package insert for Gattex (teduglutide), the most common adverse reactions across all studies are abdominal pain, injection site reactions, nausea, headaches, abdominal distension, and upper respiratory tract infection. The package insert also includes the following statement: "In the clinical studies, 13 subjects were diagnosed with polyps of the G.I. tract after initiation of study treatment. In the SBS placebo controlled studies, 1/59 (1.7%) of subjects on placebo and 1/109 (0.9%) of subjects on GATTEX 0.05 mg/kg/day were diagnosed with intestinal polyps (inflammatory stomal and hyperplastic sigmoidal after 3 and 5 months, respectively). The remaining 11 polyp cases occurred in the extension studies - 2 colorectal villous adenomas (onset at 6 and 7 months in GATTEX 0.10 and 0.05 mg/kg/day dose groups, respectively), 2 hyperplastic polyp (onset 6 months in GATTEX 0.10 mg/kg/day dose group and 24 months in GATTEX 0.05 mg/kg/day dose group), 3 colorectal tubular adenomas (onset between 24 and 29 months in GATTEX 0.05 mg/kg/day dose group), 1 serrated adenoma (onset at 24 months in GATTEX 0.05 mg/kg/day dose group), 1 colorectal polyp biopsy not done (onset at 24 months in GATTEX 0.05 mg/kg/day dose group), 1 rectal inflammatory polyp (onset at 10 months in the GATTEX 0.05 mg/kg/day dose group, and 1 small duodenal polyp (onset at 3 months in GATTEX 0.05 mg/kg/day dose group)."

